**6.2.2                    Dosage Adjustments, Delays, Rules for Withholding or Restarting, Permanent Discontinuation**

**6.2.2.1                Dose Adjustment**

A given subject should continue on the same dose level of AMG 994 throughout the study.

An exception to this may be considered when a given subject experiences a DLT or other intolerable AMG 994-related adverse event, but shows evidence of clinical benefit. The medical monitor and investigator, in consultation with the GSO, may deem it appropriate for such subjects to have a dose reduction to the immediate next lower dose. Each subject is only allowed 1 dose reduction.

No dose modifications for AMG 404 are recommended. Based on established preclinical and clinical data available from AMG 404 and other anti-PD1 therapies and

also on preclinical data from AMG 994, immune-mediated adverse reactions are expected to be associated to AMG 404 and emerging study safety data will inform any necessary revision of this initial expectation. Guidelines for withholding or discontinuing AMG 404 for immune-mediated reactions are listed in [Table 11-3](#). If AMG 404 has been withheld, treatment with AMG 404 may be resumed after the adverse event (or associated signs/symptoms/laboratory parameters) has been reduced to grade  $\leq 1$  and corticosteroid has been tapered to prednisone  $< 10$  mg or equivalent (per [Table 11-3](#), myocarditis must be resolved to grade  $< 1$ ).

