#### **6.2.2.2 Rules for Withholding or Restarting**

- AMG 994, and AMG 404 if the subject is on combination therapy, should be withheld for any DLT or any adverse event that meets the criteria of a DLT but occurs outside of the DLT windows
- AMG 994, and AMG 404 if the subject is on combination therapy, should be withheld for potential hepatotoxicity as detailed in [Table 11-2](#)
- AMG 404 alone should be withheld for immune-mediated adverse reactions as detailed in [Table 11-3](#)
- AMG 994 and/or AMG 404 should be withheld for infusion-related reactions as specified in [Table 11-4](#)

For adverse events not addressed by [Table 11-2](#), [Table 11-3](#) and [Table 11-4](#), AMG 994 and AMG 404 dosing can be resumed if the applicable event resolves to grade  $\leq 1$  or otherwise resolves to subject's baseline grade within 2 weeks. The restarting of therapy should be deemed appropriately safe by the investigator and Medical Monitor. For restart criteria following hepatotoxicity, immune-mediated reactions, and infusion-related reactions, refer to [Table 11-2](#), [Table 11-3](#) and [Table 11-4](#), respectively. For immune-mediated hepatitis, if [Table 11-2](#) and [Table 11-3](#) are both applicable, [Table 11-2](#) is to take precedence.

Subjects should not be restarted with AMG 994 and/or AMG 404 if the following treatment-related adverse events occur:

- Any grade 4 adverse events except those not considered DLT, OR
- Adverse event criteria are met for permanent withholding of AMG 994 and/or AMG 404 due to potential hepatotoxicity, immune-mediated reaction or infusion related reaction ([Table 11-2](#), [Table 11-3](#), or [Table 11-4](#), respectively). For immune-mediated hepatitis, if [Table 11-2](#) and [Table 11-3](#) are both applicable, [Table 11-2](#) is to take precedence.

If a subject experiences an adverse event meeting withholding or discontinuation criteria above from AMG 404, and if the subject is experiencing clinical benefit with AMG 994 monotherapy, a decision to have the subject continue with AMG 994 monotherapy alone, may be considered by the Amgen medical monitor in consultation with the investigator.

The reason for dose change of AMG 994 and/or AMG 404 is to be recorded on each subject's CRF.

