## **9. Statistical Considerations**

### **9.1 Statistical Hypotheses**

This is a phase 1 study and no formal statistical hypotheses will be tested.

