**AMGEN®**

**Table 11-3. Dose Modification and Toxicity Management Guidelines for Immune-related Adverse Reactions Associated With AMG 404\***

Immune-related Adverse Reactions	Severity (CTCAE Grade Version 5.0 or Specific Conditions)	AMG 404 Dose Modification	Management with Corticosteroids and/or Other Therapies	Monitor & Follow-up		
Myocarditis	Grade 1 (abnormal cardiac biomarker testing, including abnormal ECG)	Withhold	Administer corticosteroids at an initial dose of 1 to 2 mg/kg/d prednisone (or equivalent) followed by taper.	Monitor patients with cardiovascular symptoms. Ensure adequate evaluation to confirm etiology and/or exclude other causes.		
	Grade 2 (abnormal screening tests with mild symptoms)					
	Grade 3 (moderately abnormal testing or symptoms with mild activity)	Permanently discontinue				
	Grade 4 (moderate to severe decompensation, IV medication or intervention required, life-threatening conditions)					
All Other Immune-Related Adverse Reactions	Grade 3 adverse reaction involving a major organ	Withhold	Based on type and severity of adverse reaction, administer corticosteroids. Refer to ASCO Clinical Practice Guidelines for additional recommendations.	Ensure adequate evaluation to confirm etiology and/or exclude other causes.		
	Life-threatening or Grade 4 adverse reaction involving a major organ	Permanently discontinue				

Page 7 of 8

Footnotes defined on last page of this table

**Table 11-3. Dose Modification and Toxicity Management Guidelines for Immune-related Adverse Reactions Associated With AMG 404\***

Immune-related Adverse Reactions	Severity (CTCAE Grade Version 5.0 or Specific Conditions)	AMG 404 Dose Modification	Management with Corticosteroids and/or Other Therapies	Monitor & Follow-up
Recurrent or Persistent Immune-Related Adverse Reactions	Recurrence of same Grade 3 or Grade 4 adverse reaction	Permanently discontinue	Based on type and severity of adverse reaction, administer corticosteroids. Additional immunosuppressive treatment may be required.	Ensure adequate evaluation to confirm etiology and/or exclude other causes.
	Requirement for $\geq 10$ mg/day prednisone (or equivalent) for more than 12 weeks			
	Persistent grade 2 or 3 adverse reactions lasting 12 weeks or longer after last dose (ie, does not resolve to grade 0 or 1 within 12 weeks)			

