
 
General considerations:
 
Corticosteroid taper should be initiated upon improvement of signs/symptoms and/or laboratory values to Grade 1 or less. Continue corticosteroid taper over the course of at least 4 to 6 weeks.
 
If AMG 404 has been withheld, treatment with AMG 404 may be resumed after adverse event (or associated signs/symptoms/laboratory parameters) has been reduced to Grade 1 or less and corticosteroid has been tapered to prednisone <math>< 10</math> mg (or equivalent).
 
For severe and life-threatening immune-related adverse reactions, IV corticosteroids should be initiated first followed by oral corticosteroids. Other immunosuppressive treatment should be initiated if the event cannot be controlled by corticosteroids.
 
				

Page 8 of 8

ACTH = adrenocorticotrophic hormone; ADL = activities of daily living; ALT = alanine aminotransferase; ASCO = American Society of Clinical Oncology; AST = aspartate aminotransferase; CSF = cerebrospinal fluid; CTCAE = Common Terminology Criteria for Adverse Events; ECG = electrocardiogram; GI = gastrointestinal; IV = intravenous; MRI = magnetic resonance imaging; PTU = propylthiouracil; SSKI = potassium iodide; SJS = Stevens-Johnson syndrome; TEN = toxic epidermal necrolysis; ULN = upper limit of normal.

\*Recommendations adapted from the American Society of Clinical Oncology (ASCO) Clinical Practice Guidelines for the Management of Immune-Related Adverse Events in Patients Treated with Immune Checkpoint Inhibitor Therapy (Brahmer et al, 2018)

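### The grade at which AMG 404 may restart after myocarditis differs between Section 6.2.2.1 and Table 11-3, the table it cites

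*Protocol*

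**What the plan says.** Section 6.2.2.1 of the Protocol (Dose Adjustment) sets a general rule for AMG 404 withheld for an immune-mediated reaction: "treatment with AMG 404 may be resumed after the adverse event (or associated signs/symptoms/laboratory parameters) has been reduced to grade" ≤ 1, with corticosteroid tapered to a prednisone-equivalent dose under 10 mg. A parenthesis in the same sentence adds, citing Table 11-3, that "myocarditis must be resolved to grade" < 1.

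Table 11-3 (Appendix 10) deals with myocarditis in two places:

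- **Myocarditis rows.** The lowest listed severity is "Grade 1 (abnormal cardiac biomarker testing, including abnormal ECG"), and the AMG 404 action is to withhold. Grade 3 leads to permanent discontinuation. No restart level is given.
- **General considerations.** Withheld AMG 404 may be resumed once the event "has been reduced to Grade 1 or less and corticosteroid has been tapered to prednisone" < 10 mg or equivalent. No event is excepted.

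Section 6.2.2.2 (Rules for Withholding or Restarting) tells sites where to look: "For restart criteria following hepatotoxicity, immune-mediated reactions, and infusion-related reactions, refer to" Tables 11-2, 11-3 and 11-4 respectively. For an immune-mediated event such as myocarditis, that is Table 11-3.

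**The concern.** Section 6.2.2.1 attributes to Table 11-3 a condition that the table does not contain, and the table's own restart rule is looser. A site that follows Section 6.2.2.2 to the table could restart AMG 404 at grade 1 myocarditis. That is a grade at which the same table says to withhold, and one that Section 6.2.2.1 says is not low enough.

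Two sites could each follow the protocol and reach opposite decisions about re-exposure after a cardiac immune event. It would also be unclear which of them had deviated. A secondary effect is that AMG 404 exposure after myocarditis, and any recurrence, would be recorded under different rules at different sites.

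**Working it through.** No arithmetic applies. The study tests no hypotheses (Section 9.1: "This is a phase 1 study and no formal statistical hypotheses will be tested"), and no sample size, error rate or stopping boundary depends on this rule. The check is a comparison of the texts.

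**Step 1. The rules side by side for myocarditis**

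| Source | Severity needed to resume AMG 404 | Steroid condition |
|---|---|---|
| Section 6.2.2.1, general rule | grade ≤ 1 | prednisone < 10 mg or equivalent |
| Section 6.2.2.1, myocarditis exception | grade < 1 | same |
| Table 11-3, myocarditis rows | none stated; withhold at grade 1 | none stated |
| Table 11-3, general considerations | grade ≤ 1, no exception | prednisone < 10 mg or equivalent |

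**Step 2. The answer at each residual grade, steroid condition met**

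| Residual grade | Section 6.2.2.1 | Table 11-3 general considerations |
|---|---|---|
| 0 | may resume | may resume |
| 1 | may not resume | may resume |
| 2 | may not resume | may not resume |

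The texts differ only at residual grade 1.

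**Step 3. Could the exception be a misprint for ≤ 1?** If so, it would add nothing, because the same sentence already sets ≤ 1 for all events. It reads as a deliberate exception.

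**Step 4. Is the table consistent with itself?** No. The myocarditis rows withhold at grade 1, and the general considerations allow resumption at grade 1 or lower. A grade 1 event meets the severity part of the restart rule at the moment it triggers withholding, so only the steroid taper separates the two. The row on persistent reactions likewise treats grade 0 or 1 as resolved, with no myocarditis exception.

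**Step 5. Does anything else settle it?** Section 6.2.2.2 gives a precedence rule only for immune-mediated hepatitis, where Table 11-2 overrides Table 11-3. The requirement that the investigator and Medical Monitor judge a restart safe sits in the paragraph that opens with events not covered by the tables. Even if it applies here, it does not say which threshold they should use.

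**Step 6. Is this a redaction or extraction effect?** There is no redaction marker in the myocarditis rows or the general considerations, and the restart sentence is complete. The grade 2 action cell is blank in the extracted text and is probably merged with the grade 1 cell. The conflict at grade 1 does not depend on it.

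**The case against.** The best counter-argument is that the table already implies the stricter threshold. A subject still at grade 1 still meets the myocarditis row's condition for withholding. Among the organ-specific rows with numerical triggers, this is the only one that withholds at grade 1: pneumonitis, colitis, hepatitis and nephritis start at grade 2, and skin at grade 3. On this view Section 6.2.2.1 simply spells out what the row means, a specific rule qualifies a permissive general note, and only a cross-reference is missing. Harm would require a site to miss Section 6.2.2.1 and also disregard the row.

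The implication is real, but it does not remove the problem. It shows that the row conflicts with the general note in the same table. The row gives no restart level, the general note is the only place in the table that does, and Section 6.2.2.2 directs sites there. The note is permissive, but permission to resume at grade 1 still contradicts a statement that grade 1 is not low enough.

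Three narrower points stand:

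- The disagreement is confined to residual grade 1. Subjects who reach grade 0, or who are still at grade 2, get the same answer from both texts.
- The general considerations call for a steroid taper of at least 4 to 6 weeks, so a restart at grade 1 would not be immediate.
- The effect on cross-site data is secondary, and no figure supports it.

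**Conclusion.** The concern holds. Section 6.2.2.1 and Table 11-3 give different restart thresholds for AMG 404 after myocarditis, and the table does not contain the exception attributed to it. This is an internal inconsistency in a safety rule, and it should be corrected.

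It affects any subject withheld for grade 1 or grade 2 myocarditis who is at grade 1 when a restart is considered. Including grade 2 assumes that its blank action cell reads as withhold. The documents give no myocarditis rate, so the number cannot be calculated. It is expected to be small, but the event is serious, and the study plans approximately 30 sites that would each have to interpret the rule. No planned estimate, analysis set or boundary changes.

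**What to change.** The sponsor's clinical team should reconcile three places: the parenthesis in Section 6.2.2.1, the myocarditis rows of Table 11-3, and the restart bullet in that table's general considerations. One threshold for resuming AMG 404 after myocarditis should appear in all of them, and the citation in Section 6.2.2.1 should point to text that states it. This review does not say which threshold is right.

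The cost is one line in an amendment and a notification to sites. No analysis or sample size changes.

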#### **6.2.2.2 Rules for Withholding or Restarting**

- AMG 994, and AMG 404 if the subject is on combination therapy, should be withheld for any DLT or any adverse event that meets the criteria of a DLT but occurs outside of the DLT windows
- AMG 994, and AMG 404 if the subject is on combination therapy, should be withheld for potential hepatotoxicity as detailed in [Table 11-2](#)
- AMG 404 alone should be withheld for immune-mediated adverse reactions as detailed in [Table 11-3](#)
- AMG 994 and/or AMG 404 should be withheld for infusion-related reactions as specified in [Table 11-4](#)

For adverse events not addressed by [Table 11-2](#), [Table 11-3](#) and [Table 11-4](#), AMG 994 and AMG 404 dosing can be resumed if the applicable event resolves to grade  $\leq 1$  or otherwise resolves to subject's baseline grade within 2 weeks. The restarting of therapy should be deemed appropriately safe by the investigator and Medical Monitor. For restart criteria following hepatotoxicity, immune-mediated reactions, and infusion-related reactions, refer to [Table 11-2](#), [Table 11-3](#) and [Table 11-4](#), respectively. For immune-mediated hepatitis, if [Table 11-2](#) and [Table 11-3](#) are both applicable, [Table 11-2](#) is to take precedence.

Subjects should not be restarted with AMG 994 and/or AMG 404 if the following treatment-related adverse events occur:

- Any grade 4 adverse events except those not considered DLT, OR
- Adverse event criteria are met for permanent withholding of AMG 994 and/or AMG 404 due to potential hepatotoxicity, immune-mediated reaction or infusion related reaction ([Table 11-2](#), [Table 11-3](#), or [Table 11-4](#), respectively). For immune-mediated hepatitis, if [Table 11-2](#) and [Table 11-3](#) are both applicable, [Table 11-2](#) is to take precedence.

If a subject experiences an adverse event meeting withholding or discontinuation criteria above from AMG 404, and if the subject is experiencing clinical benefit with AMG 994 monotherapy, a decision to have the subject continue with AMG 994 monotherapy alone, may be considered by the Amgen medical monitor in consultation with the investigator.

The reason for dose change of AMG 994 and/or AMG 404 is to be recorded on each subject's CRF.

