### **6.1.7 Excluded Treatments, Medical Devices, and/or Procedures During Study Period**

Any anti-tumor therapy other than the investigational product, including cytotoxic and/or cytostatic drugs, hormonal therapy, systemic corticosteroids (except for subjects who were receiving  $\leq 10$  mg prednisone or equivalent at the time of enrollment are permitted to remain on it), immunotherapy or any biological response modifiers, any other investigational agent, and other immunosuppressive therapies are excluded.

Primary prophylactic use of hematopoietic growth factors such as granulocyte-colony stimulating factor is not encouraged during the DLT-evaluation period. Once the DLT evaluation period is complete, the use of growth factors can be allowed after discussion with the Amgen medical monitor.

Administration of systemic corticosteroids, immunomodulators, and hormonal replacement therapy for the management of toxicities (eg, immune-related adverse events) is allowed; however, AMG 994 and AMG 404 must be discontinued if  $\geq 10$  mg per day prednisone or equivalent is continued for more than 12 weeks. Corticosteroids with no or minimal systemic effect (eg, topical, inhalation) are allowed.

Any live vaccine therapies for the prevention of infectious disease are not allowed (except administration of the inactive influenza vaccine).

Radiotherapy is not permitted except for palliation of symptoms and should be discussed with the sponsor's Medical monitor first. Investigators should ensure that the need for radiation does not indicate progressive disease and that for subjects with measurable disease, radiation is not to the sole site of measurable disease.

The following procedures should also not be undertaken within the timeframes specified prior to enrollment and during the study:

- Participation in any investigational study (drug or device) within [REDACTED]  
[REDACTED]
- Major surgery within [REDACTED]
- Enrollment into another investigational drug or device study

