### **Dose-Limiting Toxicity**

All events will be graded using the CTCAE version 5.0. The occurrence of any of the following events during the first or second DLT evaluation period will be considered a DLT, excluding events clearly related to disease progression or intercurrent illness:

- Any grade 5 event
- Grade 4 neutropenia or thrombocytopenia of any duration
- Grade 3 thrombocytopenia with clinically significant bleeding or lasting > 7 days
- Febrile neutropenia
- Grade 4 anemia
- Grade 3 or 4 non-hematologic toxicity, with the following exceptions:
  - DLT Exemption: Grade 3 nausea/vomiting or diarrhea < 72 hours in the absence of maximal medical therapy
  - DLT Exemption: Grade 3 fatigue < 1 week

- DLT Exemption: Asymptomatic grade 3 electrolyte abnormalities that last < 72 hours, are not clinically complicated, and resolve spontaneously or respond to conventional medical interventions
- DLT Exemption: Grade 3 amylase or lipase elevations, as per CTCAE version 5.0, grade 4 elevations in amylase and lipase are defined as being associated with signs or symptoms of pancreatitis
- DLT Exemption: Other laboratory parameters of grade 3, not considered clinically relevant, and improved to grade  $\leq 2$  within 72 hours.
- Any grade 3 event requiring hospitalization
- Recurrent grade 2 pneumonitis
- Delay in cycle 2 treatment for  $> 14$  days due to an adverse event in the dose escalation portion of the study due to study drug-related toxicity, except for immune-mediated toxicities as outlined in [Table 11-3](#) where a longer timeframe is specified
- Any other event requiring permanent discontinuation of AMG 994 (for example, as specified in [Table 11-4](#), Infusion-Related Reactions)

[figure not shown]
The cumulative adverse event profile will be taken into consideration when making decisions on dose escalation and on any other dose-level or safety review.

Any subject meeting the criteria for Hy's Law case (ie, severe drug-induced liver injury) will be considered a DLT. A Hy's Law case is defined as: AST or ALT values of  $\geq 3 \times$  ULN AND with serum TBL of  $> 2 \times$  ULN without signs of cholestasis and with no other clear alternative reason to explain the observed liver-related laboratory abnormalities (see Section [6.2.3](#) for hepatotoxicity management and Section [11.7](#) for further explanation of Hy's law case and Management of Hepatic Function).

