	Grade 3 (increase of 7 or more stools per day over baseline, incontinence; hospitalization indicated, severe increase in ostomy output compared with baseline, limiting self-care ADL)			
	Grade 4 (life-threatening consequences; urgent intervention indicated)	Permanently discontinue		

Page 2 of 8

Footnotes defined on last page of this table

**Table11-3. Dose Modification and Toxicity Management Guidelines for Immune-related Adverse Reactions Associated With AMG 404\***

Immune-related Adverse Reactions	Severity (CTCAE Grade Version 5.0 or Specific Conditions)	AMG 404 Dose Modification	Management with Corticosteroids and/or Other Therapies	Monitor & Follow-up
Hepatitis	Grade 2 (asymptomatic, AST or ALT > 3.0 to $\leq$ 5 x ULN and/or total bilirubin > 1.5 to $\leq$ 3 x ULN [for patients with values < ULN at baseline])	Withhold	Administer corticosteroids at an initial dose of 0.5 to 1 mg/kg/d prednisone (or equivalent) followed by taper.	Monitor with liver function tests more frequently until returned to baseline or stable.
	Grade 3 (symptomatic liver dysfunction, fibrosis by biopsy, compensated cirrhosis, reactivation of chronic hepatitis [AST or ALT 5-20 x ULN and/or total bilirubin 3-10 x ULN])	Permanently discontinue	Administer corticosteroids at an initial dose of 1 to 2 mg/kg/d prednisone (or equivalent) followed by taper. Consider mycophenolate mofetil if refractory to corticosteroids or no improvement after 3 days.	
	Grade 4 (decompensated liver function eg, ascites, coagulopathy, encephalopathy, coma [AST or ALT > 20 x ULN and/or total bilirubin > 10 x ULN])		Administer corticosteroids at an initial dose of 2 mg/kg/d prednisone (or equivalent) followed by taper. Consider mycophenolate mofetil if refractory to corticosteroids or no improvement after 3 days.	

Page 3 of 8

Footnotes defined on last page of this table

**Table 11-3. Dose Modification and Toxicity Management Guidelines for Immune-related Adverse Reactions Associated With AMG 404\***

Immune-related Adverse Reactions	Severity (CTCAE Grade Version 5.0 or Specific Conditions)	AMG 404 Dose Modification	Management with Corticosteroids and/or Other Therapies	Monitor & Follow-up

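### Section 6.2.2.2 gives conflicting instructions for AMG 994 when a grade 3 immune-mediated reaction also meets a DLT criterion, and no precedence or AMG 994 restart rule settles it

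*Protocol*

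**What the plan says.** **Withholding.** Section 6.2.2.2 lists four bullets. Under the first, AMG 994, plus AMG 404 for a subject on the combination, "should be withheld for any DLT or any adverse event that meets the criteria of a DLT but occurs outside of the DLT windows". Under the third, "AMG 404 alone should be withheld for immune-mediated adverse reactions as detailed in" Table 11-3.

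**DLT definition.** Section 6.2.1 lists "Grade 3 or 4 non-hematologic toxicity, with the following exceptions". The exceptions cover short-lived gastrointestinal events, fatigue, electrolyte changes, amylase or lipase, and other minor laboratory findings. The only immune carve-out in the DLT list, "except for immune-mediated toxicities as outlined in" Table 11-3, is attached to the cycle 2 delay criterion.

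**Table 11-3 (Appendix 10).** It has one dose-modification column, headed for AMG 404. It includes grade 3 rows, for example "Grade 3 (increase of 7 or more stools per day over baseline, incontinence; hospitalization indicated".

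**Precedence and restart.** Section 6.2.2.2 ranks Table 11-2 over Table 11-3 for immune-mediated hepatitis and ranks nothing else. It sends restart after an immune-mediated reaction to Table 11-3. Its general restart rule covers only events that Tables 11-2 to 11-4 do not address.

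**Prolonged steroids.** Section 6.1.7 allows steroids for managing toxicity; "however, AMG 994 and AMG 404 must be discontinued if" prednisone of at least 10 mg per day runs beyond 12 weeks. In Table 11-3 the same trigger, "mg/day prednisone (or equivalent) for more than 12 weeks", leads to permanent discontinuation in the AMG 404 column. Section 6.2.2.2 adds a continuation clause for a subject who meets AMG 404 withholding or discontinuation criteria and is benefiting on AMG 994 given by itself: "a decision to have the subject continue with AMG 994 monotherapy alone, may be considered by the Amgen medical monitor". The monitor is to consult the investigator.

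**The concern.** The first and third bullets are written as free-standing rules, yet their triggers overlap. One turns on meeting a DLT criterion and the other on the event being a listed immune-mediated reaction. A serious immune reaction can be both, and the bullets then differ on whether AMG 994 continues.

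This is a first-in-human study in which AMG 994 dose is the variable explored and AMG 404 is fixed. Whether AMG 994 continues through a serious immune reaction bears on subject safety, on AMG 994 exposure, and on attribution of later events. SAP Sections 9.6.2 and 9.6.7 summarise events leading to interruption or withdrawal of product, cumulative dose and dose modifications. Those summaries would mix cases handled under different rules. The first bullet also applies outside the DLT windows, so the overlap is not confined to the DLT period.

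**Working it through.** The plan gives no figure here and none can be derived, so the check is a cross-reading.

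**Step 1: is a grade 3 immune reaction a DLT-type event?** Take grade 3 immune-mediated colitis on the combination that outlasts the 72-hour diarrhea exemption. It is non-hematologic and grade 3, and none of the exceptions in Section 6.2.1 fits. It meets the criterion.

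**Step 2: which bullets apply, and what do they say?**

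| Rule | AMG 404 | AMG 994 |
|---|---|---|
| 6.2.2.2, first bullet (meets a DLT criterion) | withhold | withhold |
| 6.2.2.2, third bullet with Table 11-3 | withhold | not withheld |

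The rules agree on AMG 404 and differ on AMG 994.

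**Step 3: which Table 11-3 rows are affected?**

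- Grade 3 with AMG 404 withheld: colitis/diarrhea, rash or suspected SJS/TEN, and other reactions involving a major organ. These three rows are in direct conflict. For colitis I read the withhold entry as spanning grades 2 and 3, because the grade 3 cell is blank in the extracted table and permanent discontinuation is entered at grade 4.
- AMG 404 permanently discontinued: examples are grade 3 and 4 pneumonitis, grade 3 nephritis lasting more than 3 days, grade 3 and 4 myocarditis, endocrine events not responding to therapy, and grade 4 other reactions. Recurrent grade 2 pneumonitis, itself a named DLT, is also here. The table says nothing on AMG 994 in these rows, which is a gap and not an opposite instruction.
- Outside the overlap: hepatitis where Tables 11-2 and 11-3 both apply, and grade 3 events under a DLT exemption.

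**Step 4: does any other text decide it?** The hepatitis precedence sentence does not reach these events. The bar on restarting after treatment-related grade 4 events names AMG 994 and/or AMG 404, so it does not say which drug. The continuation clause covers only subjects benefiting on AMG 994 monotherapy and leaves it to the medical monitor's discretion.

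**Step 5: restart.** If the first bullet stops AMG 994 for an immune reaction, Section 6.2.2.2 refers to Table 11-3, whose resumption criteria are for AMG 404 only. The general restart rule excludes events that Table 11-3 addresses. No AMG 994 restart criterion remains. Section 6.2.2.1 allows one AMG 994 dose reduction after a DLT with clinical benefit, but does not say when dosing may resume.

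**Step 6: the 12-week steroid trigger.**

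| Passage | AMG 404 | AMG 994 |
|---|---|---|
| 6.1.7 | must be discontinued | must be discontinued |
| Table 11-3 | permanently discontinue | silent |
| 6.2.2.2 continuation clause | withholding or discontinuation criteria met | may be continued alone, conditionally |

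A site can satisfy Section 6.1.7 and Table 11-3 together by stopping both drugs. The inconsistency appears when the continuation clause is applied to a subject who has met the steroid trigger.

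**The case against.** The best reply is that the bullets are layered. The first governs anything that meets a DLT criterion. The third keeps its own work for Table 11-3 events that are not DLTs, such as a first grade 2 pneumonitis, grade 2 colitis, grade 2 nephritis or grade 1 myocarditis. Section 6.2.2.1 supplies a rationale, since immune reactions are expected to be associated with AMG 404. The continuation clause would then allow both drugs to be withheld before a decision on AMG 994. This is coherent, but no text states it. The third bullet confines withholding to AMG 404, and Table 11-3 includes grade 3 withhold rows. Section 6.2.2.1 also describes the association with AMG 404 as an expectation open to revision.

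Other parts of the reply stand:

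- The steroid passages are a weaker inconsistency. A conditional permission does not clearly override a mandatory stop.
- Section 4.1 sends each DLT or suspected DLT in Part 1 to the sponsor's safety group and medical monitor, which limits divergence between sites.
- A reader might infer that nearly every grade 3 or 4 row of Table 11-3 carries opposite instructions. Step 3 shows that it does not.
- A reader might also infer that DLT counts, and so the dose-escalation model, are compromised. They are not: a qualifying event inside the window is a DLT by its grade, whatever is done with AMG 994.
- Nor does the withholding conflict directly change the primary-endpoint component on events requiring permanent discontinuation. Only the steroid passages bear on that directly.

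**Conclusion.** Wrong as written: an internal inconsistency, not a design choice. For a non-exempt grade 3 immune-mediated reaction on the combination, Section 6.2.2.2 gives two instructions for AMG 994 and no rule for choosing between them. The direct conflict is confined to three grade 3 rows of Table 11-3. Around it lie the table's silence on AMG 994 in the AMG 404 discontinuation rows, the missing AMG 994 restart criterion, and the weaker mismatch on prolonged steroids.

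The consequence is that subjects with the same toxicity can get different AMG 994 handling and exposure, depending on which bullet is followed. That they will do so is not shown. The documents give no incidence of such reactions, so no number of affected subjects can be stated. The conclusion rests on the current wording of Sections 6.1.7, 6.2.1 and 6.2.2.2 and of Table 11-3, including the colitis reading in step 3. It takes no position on which instruction is clinically right.

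**What to change.** Reconcile the passages in one amendment:

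1. In Section 6.2.2.2, state which bullet governs AMG 994 when a Table 11-3 reaction also meets a DLT criterion, for withholding and for restart. The hepatitis sentence is a model.
2. In the same section, say which drug the grade 4 restart bar covers when the event is immune-mediated.
3. Make Section 6.1.7, the 12-week steroid row of Table 11-3 and the continuation clause consistent on which drug or drugs they cover.

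An AMG 994 column in Table 11-3 would be a clear way to show the result but is optional. The sponsor's safety team decides which instruction stands. The cost is a wording amendment and a letter to sites, with no new procedures, data or subjects.
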